# Secondary:

- 1. Proportion of patients discharged with a catheter (this is essentially the proportion of patients who failed the voiding trial)
- 2. Proportion of patients who reported *any* UTI within the six-week post-operative period. The number of UTIs reported by each patient during that period will also be recorded.
- 3. Proportion of patients with emergency room visits or unexpected visits to the Urogynecology clinic for voiding dysfunction or suspected infection, within the sixweek post-operative period. The number of ER visits or unexpected clinic visits will also be recorded.
- 4. Time-to-catheterization post-discharge: This is the number of days from discharge to catheterization (within the 6-week period post-surgery). Subjects who are not catheterized by the end of the follow-up period will be considered 'censored'.
- 5. Patient satisfaction with postoperative bladder function (measured at baseline, 2-weeks post-op and 6 weeks post-op) using:
  - a. American Urological Association Symptom Score (AUASS)
  - b. Urinary Distress Inventory (UDI-6)

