#### **Secondary Outcomes**

- 1. Proportion of patients discharged with a catheter (this is essentially the proportion of patients who failed the voiding trial)
- 2. Proportion of patients who reported *any* UTI within the six-week post-operative period. The number of UTIs reported by each patient during that period will also be recorded.
- Proportion of patients with emergency room visits or unexpected visits to the Urogynecology clinic for voiding dysfunction or suspected infection, within the sixweek post-operative period. The number of ER visits or unexpected clinic visits will also be recorded.
- 4. Time-to-catheterization post-discharge: This is the number of days from discharge to catheterization (within the 6-week period post-surgery). Subjects who are not catheterized by the end of the follow-up period will be considered 'censored'.
- 5. Patient satisfaction with postoperative bladder function (measured at baseline, 2-weeks post-op and 6 weeks post-op) using:
  - c. American Urological Association Symptom Score (AUASS)
  - d. Urinary Distress Inventory (UDI-6)

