## **Statistical Methods:**

1. For the primary objective:

The test for non-inferiority will be carried out using a two-tailed 95% confidence interval for the difference in the rate of catheterization between the two voiding methods, within the six-week post-operative period,  $\delta$  ( $\delta$ =rate of catheterization in the FAST voiding trial – rate of catheterization in the Traditional voiding trial). This difference,  $\delta$ , is the margin of non-inferiority and will be set at 10%. If the upper confidence limit for the difference is  $<\delta$  ( $\ge\delta$ ) then we will conclude that the FAST voiding trial is non-inferior (inferior) to the Traditional voiding trial.

The test for non-inferiority will be performed only for the primary outcome variable of interest, i.e., catheterization within the six-week post-operative period among subjects who were discharged without needing a urinary catheter.

The test for non-inferiority will also be performed according to surgery type (the stratification variable).

- For the secondary objectives:
  - a. The chi-square test or Fisher's exact test, as appropriate, will be used to compare the two voiding methods with respect to the proportion of subjects who are sent home with a catheter due to failure of their voiding trial, post-surgery.
  - b. The chi-square test or Fisher's exact test, as appropriate, will be used to compare the two voiding methods with respect to the proportion of subjects who present with any UTI within the six-week post-operative period. If feasible, the incidence of UTIs will be compared between the two voiding methods using the Incidence Density Ratio Method, or if feasible, Poisson regression methods.
  - c. The chi-square test or Fisher's exact test, as appropriate, will be used to compare the two voiding methods with respect to the proportion of subjects who present to the emergency room or the urogynecology clinic (unexpectedly) due to voiding dysfunction or suspected infection, within the six-week post-operative period. If feasible, the incidence of ER visits or unexpected clinic visits will be compared between the two voiding methods using the Incidence Density Ratio Method, or if feasible, Poisson regression methods.

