  - d. The Kaplan-Meier product limit method will be used to estimate time-to-catheterization post-discharge and the two groups (Traditional Retrograde vs. FAST) will be compared using the log-rank test. Median time-to-catheterization will be estimated along with their corresponding 95% confidence intervals. The feasibility of this analysis will depend on the observed catheterization rates.
  - e. A mixed models approach to repeated measures analysis of variance (MM-RMANOVA) will be carried out, separately, for each of the two measures of patient satisfaction with post-operative bladder function (AUASS and UDI-6). Each model will examine if the patterns of change in satisfaction scores across

Version Date: 2/26/16 Page 11 of 25

time (baseline, 2 weeks post-op and 6 weeks post-op) differ between the two voiding methods. The models will include voiding group (Traditional/FAST), time (baseline, 2 weeks post-op and 6 weeks post-op) and a group-by-time interaction term. Data transformations may be employed if standard model assumptions are not met. If no suitable transformations are found, then appropriate non-parametric methods may be used instead.

A secondary analysis using logistic regression, will be carried out for each of the aims 2a, 2b and 2c, including explanatory variables such as age, site, and surgery type (sling vs. no sling).

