#### Sample Size Considerations:

The proposed sample size for this one year study is a total of 154 evaluable subjects (n=77 randomized to each voiding group). A subject will be "evaluable" if she gets randomized and is able to undergo the voiding trial. A subject who is not able to undergo the voiding trial is considered "not evaluable" and would not be included in the analysis.

The study will be designed as a non-inferiority trial, where the FAST voiding trial will be considered non-inferior to the Traditional voiding trial if the difference in the rate of catheterization between the two groups within the six-week post-operative period among patients discharged without a catheter is less than  $\delta$ =10% (i.e.  $\delta$ =10%, the margin of non-inferiority). More formally, if the rates of catheterization during the six-week post-operative period are p\_F and p\_T, respectively for the FAST and Traditional voiding methods, then the null (Ho) and alternative hypotheses (HA) are:

$$H_0$$
:  $d = p_F - p_T \ge \delta$  vs.  
 $H_A$ :  $d = p_F - p_T < \delta$ 

Based on the investigators' clinical experience, it can be reasonably assumed that among those who pass the Traditional retrograde fill voiding trial, the rate of catheterization during the six-week post-operative period is about 5%. Further assuming that the rate of catheterization among those who pass the FAST voiding trial is the same as in the traditional voiding test (i.e. 5% as well), and using a non-inferiority margin, $\delta$ , of 10%, then a sample size of 59 per group (n=118 total) will yield 80% power to determine that the FAST voiding trial is not inferior to the Traditional voiding trial (alpha=0.05).

Based on published manuscripts, about 30% of evaluable patients will fail either voiding trial, that is, approximately 30% in the traditional retrograde fill voiding trial arm will fail the test and similarly, approximately 30% in the FAST voiding trial arm will fail the test. Therefore, in order to obtain 118 subjects who pass the voiding test (59 per group), we would need to have a total of 154 subjects (118 x 1.3=154).

Randomized subjects will fall into three groups:

- 1. Subjects with a complication at surgery that would require prolonged catheterization immediately postoperative.
- 2. Subjects who fail either voiding test and are discharged home with a catheter (expected to be 25-26% based on pusblished manuscripts)

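### If women have repeat UTIs or repeat unplanned visits, the planned incidence density ratio or Poisson comparison understates the standard error, and the plan names no within-woman variance

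*Combined protocol and SAP*

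**What the plan says.** Section 10 and the Secondary Outcomes list in Section 12 define the UTI and unplanned-visit outcomes as proportions of women with any event, and add counts. For UTIs: "The number of UTIs reported by each patient during that period will also be recorded". For visits: "The number of ER visits or unexpected clinic visits will also be recorded".

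Under Statistical Methods, secondary objectives b and c, the first-named comparison is a chi-square or Fisher's exact test on one yes/no result per woman. For UTIs this is "the proportion of subjects who present with any UTI within the six-week post-operative period". A count comparison follows, conditional on feasibility: "the incidence of UTIs will be compared between the two voiding methods using the Incidence Density Ratio Method, or if feasible, Poisson regression methods". The sentence for visits is the same in substance: "the incidence of ER visits or unexpected clinic visits will be compared between the two voiding methods using the Incidence Density Ratio Method", again with Poisson regression as the alternative.

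The adjusted analysis is binary: "A secondary analysis using logistic regression, will be carried out for each of the aims 2a, 2b and 2c".

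No sentence in Section 12 mentions overdispersion, a robust or scaled variance, a negative binomial model or a woman-level effect for these counts. The only fallback for failed model assumptions belongs to the AUASS and UDI-6 mixed models.

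**The concern.** The any-event outcome already has its own test, so the count comparison adds information only through repeat events (and follow-up time). Repeat events are also where the plain form of both named methods is weakest. Each sets the variance of the count equal to its mean, so ten visits by five women carry the same weight as ten visits by ten women. Clustering is plausible for visits, because one unresolved voiding problem can bring a woman back several times. Objective 2c also pools women discharged with and without a catheter, who may differ in risk.

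At stake is the credibility of two rate ratios. The Brief Summary anticipates no difference in UTIs or unplanned visits, and Section 17 names retention and UTI as the risks. A chance difference in event rates, declared significant because of a few women with several events, would sit awkwardly beside a null chi-square test on the same outcome.

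**Working it through.** The documents give no figure for the count analyses, so there is none to reproduce.

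**Inputs from the documents**
- Women per arm: 77 (Sample Size Considerations, "n=77 randomized to each voiding group"), all taken as analysed.
- Share of women affected, p: 6% to 20%. Section 17 gives this as infection risk after temporary catheter placement. It is a proxy for the UTI rate and a looser one for visits.
- Two-sided 5% level. The plan states it for the primary sample size; it is assumed here for the secondary tests.

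**Assumed, because the documents are silent:** the number of events K in an affected woman.

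**Step 1: variance relative to the mean.** If a woman is affected with probability p and then has K events, variance/mean = E[K²]/E[K] − p·E[K]. A Poisson standard error is right only when this equals 1.
- No repeats (K = 1): 1 − p, which is 0.94, 0.90 and 0.80 at p = 6%, 10% and 20%. The Poisson standard error is slightly too large.
- A quarter have a second event: E[K] = 1.25, E[K²] = 0.75×1 + 0.25×4 = 1.75. Ratio 1.40 − 1.25p = 1.33, 1.28, 1.15.
- Half have a second event: E[K] = 1.5, E[K²] = 2.5. Ratio 1.67 − 1.5p = 1.58, 1.52, 1.37.
- Half have two extra events: E[K] = 2, E[K²] = 0.5×1 + 0.5×9 = 5. Ratio 2.5 − 2p = 2.38, 2.30, 2.10. The standard error is too small by a factor of about √2.3 = 1.5.
- Geometric with mean 2: E[K²] = 6. Ratio 3 − 2p = 2.88, 2.80, 2.60.

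**Step 2: false-positive rate, large-sample approximation.** 2·[1 − Φ(1.96/√ratio)]. At p = 10%:
- no repeats: 1.96/√0.90 = 2.07, giving 3.9%
- a quarter with a second event: 1.96/√1.275 = 1.74, giving 8.3%
- half with a second event: 1.96/√1.517 = 1.59, giving 11%
- geometric, mean 2: 1.96/√2.80 = 1.17, giving 24%

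**Step 3: simulation.** Counts are small: 77×0.06 ≈ 4.6 affected women per arm, up to 77×0.20 ≈ 15. The approximation was therefore checked with no true difference between arms (40,000 simulated trials per setting for the first four rows). The Wald test uses log(a/b)/√(1/a + 1/b) and the score test (a − b)/√(a + b), where a and b are total events per arm. The robust Wald test uses the between-woman variance.

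| Pattern in affected women | Wald, p = 6 / 10 / 20% | Score, p = 6 / 10 / 20% | Robust, p = 6 / 10 / 20% |
|---|---|---|---|
| No repeats | 1.3 / 2.7 / 2.7% | 4.0 / 3.8 / 3.2% | 1.9 / 3.6 / 4.6% |
| 25% have a second event | 4.8 / 7.0 / 6.2% | 8.2 / 8.5 / 6.7% | 3.0 / 4.6 / 4.7% |
| 50% have a second event | 8.2 / 9.9 / 8.5% | 11.8 / 11.4 / 9.0% | 3.5 / 4.1 / 4.4% |
| 50% have two extra events | 17.5 / 18.8 / 17.2% | 21.3 / 20.1 / 17.7% | 5.9 / 4.9 / 4.8% |
| Geometric, mean 2 | about 21-23% | about 22-25% | up to about 7% |

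If only 10% of affected women have a second event, the Wald test stays at 2.6 / 4.4 / 4.3%. Chi-square on any event stays at 4.8% to 5.5% in the four non-geometric patterns; repeats cannot affect it, since it uses only whether a woman had an event.

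**The case against.** A reader might infer that the planned standard errors are too small as a matter of fact. The documents do not support that. They give no repeat rate for either outcome over six weeks, and with few or no repeats the plain Wald test is at or below its nominal level. The larger figures need a heavy tail: a geometric count with mean 2 means that half of affected women have a repeat and a quarter have three or more events. Section 17 also reports that FAST patients in earlier studies had no emergent or unexpected emergency room visits. That points to few ER visits, but does not cover unexpected clinic visits.

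A reader might also infer that the plan has chosen an invalid method. It has not: Poisson regression is named generically, which leaves room for a robust or scaled variance, and the crude rate ratio is a sound estimate. What is missing is the variance.

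Finally, a reader might take the trial's UTI and visit conclusions as a whole to be at risk. The count analyses are secondary and conditional on feasibility. The per-woman tests come first and are sound, and the logistic models are binary.

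All of this stands and sets the limits of the point. It does not remove it. Counts are recorded so that repeats can be used, the plain incidence density ratio is named first, and nothing in the plan protects its interval if repeats occur.

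**Conclusion.** The point holds conditionally, as an omission. The plain methods are miscalibrated in a direction that depends on data not yet seen: slightly conservative without repeats, anticonservative once repeats are common. At nominal 5%, taking the Wald and score tests together, the false-positive rate is about:
- 1-4% with no repeats
- 5-8% if a quarter of affected women have a second event
- 8-12% if half do
- 21-25% for a geometric count with mean 2

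These figures rest on 77 women per arm, 6% to 20% affected (a proxy) and assumed repeat patterns. The effect is confined to the rate comparisons under secondary objectives b and c. The non-inferiority conclusion and every any-event analysis stand as planned. Because the repeat rate is unknown in advance, the variance should be fixed before the data are seen.

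**What to change.** In Statistical Methods, secondary objectives b and c, replace the incidence density ratio and Poisson sentences with wording such as: *The number of UTIs (visits) per woman will be compared between arms by a log-linear (Poisson) rate model with log follow-up time as offset and robust (sandwich) variance, with the woman as the unit; the rate ratio and its 95% confidence interval will be reported. The proportion of women with any event remains the main comparison.* This interval takes the place of the plain incidence density ratio interval; the crude rate ratio itself may still be shown.

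The cost is a change of wording and one option in the same software procedure, with no new data, visits or participants. The interval will be wider when events cluster. The robust test is itself approximate with so few affected women: its false-positive rate was about 2-7% across these scenarios, so it should not be presented as exact.

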Under anesthesia the bladder has a capacity ranging from 700-1000cc. Awake the bladder capacity is less, secondary to patient's urge to urinate secondary to bladder fullness which on average occurs at 300cc. The FAST voiding trial method showed that 500cc is an acceptable and safe amount in the bladder after midurethral sling placement if the patient states her FOS is >50% preoperatively.

All patients discharged with a Foley catheter will be provided with the hospital's standard teaching for home care of Foley catheter. All patients will be instructed to notify their physician if they had any postoperative problems, specifically difficult voiding, or signs or symptoms of infection. All patients will be scheduled for a follow-up visit with the surgeon at 2 weeks and at 6 weeks postoperatively. This is standard in our practice regardless of participation in the research study. At these visits, patients will have another PVR obtained by bladder scan. The UDI-6 and AUASS will be re-administered at those visits as well.

We will collect information from their outpatient electronic medical records. Information collected will include age, race, body mass index, parity, severity of prolapse preopreatively, preoperative Urodynamics (UDS) including: cough stress test, leak point pressures, Urethral pressure profiles, presence of detrusor instability, use of antiincontinence medications, surgical history, urinalysis and PVR.

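### The lead comparison of voiding-trial failure (aim 2a) is unadjusted, and no model in section 12 names the PVR that section 11 lists for collection

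*Combined protocol and SAP*

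**What the plan says.** Section 11 (Research Procedures, after the description of the FAST method) introduces the chart data: "We will collect information from their outpatient electronic medical records". The list ends with "use of antiincontinence medications, surgical history, urinalysis and PVR". The word preoperative is attached to prolapse severity and urodynamics, not directly to PVR. The paragraph before it describes the PVR at the 2- and 6-week visits as a further one, so a preoperative value is the natural reading, though not an explicit one.

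Section 12 (Statistical Methods) compares the two methods by chi-square or Fisher's exact test on each of three secondary outcomes:

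- Aim 2a: "with respect to the proportion of subjects who are sent home with a catheter due to failure of their voiding trial, post-surgery"
- Aim 2b: "with respect to the proportion of subjects who present with any UTI within the six-week post-operative period"
- Aim 2c: "with respect to the proportion of subjects who present to the emergency room or the urogynecology clinic (unexpectedly"

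After these comes the adjusted analysis: "A secondary analysis using logistic regression, will be carried out for each of the aims 2a, 2b and 2c". The covariates for that model are given as examples only, by the phrase "including explanatory variables such as age, site, and surgery type (sling vs. no sling". PVR is named in no model in section 12. Under Randomization, allocation is 1:1 and stratified by site and, within site, by surgery with or without a sling.

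**The concern.** Aim 2a is the secondary outcome that shows whether FAST spares women a catheter at discharge. In the traditional arm, failure is decided by how well the bladder empties on postoperative day 1, and preoperative PVR is the listed baseline value closest to that function. Section 7 excludes only women with baseline retention who cannot urinate without a catheter, so PVR can still vary among those enrolled.

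An unadjusted lead test leaves any chance imbalance in baseline emptying in the estimate. It also makes no use of the two stratification factors. Because the covariate list for the secondary model is open, PVR may be added to it, but nothing commits the analyst in advance. A choice made after the results are seen would carry less weight.

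**Working it through.** **The plan's own figures.** No power or precision is stated for aims 2a to 2c. The stated size belongs to the primary outcome: n per group = (1.645 + 0.842)² × 2 × 0.05 × 0.95 / 0.10² = 58.7, that is 59, at one-sided alpha 0.05. Then 118 × 1.3 = 153.4, that is 154. Whether that alpha and that inflation suit the primary analysis is a separate question. Here only the resulting 77 per arm is used.

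**Events available.** Sample Size Considerations gives about 30% failure, and 25-26% a few lines later.

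- Aim 2a: 154 × 0.30 = 46 events; at 25-26%, 39 to 40. With five coefficients (group, site, surgery type, age, PVR) that is about 8 to 9 events per coefficient.
- Aim 2b: section 17 gives a 6% to 20% infection risk with temporary catheterisation. If that is taken as the UTI rate (an assumption), 154 × 0.06 = 9 and 154 × 0.20 = 31 events.

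**Precision without adjustment.** At 30% in both arms, the 95% half-width for the difference is 1.96 × √(2 × 0.30 × 0.70 / 77) = 14.5 percentage points.

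**Gain from PVR.** The documents give no prognostic strength. Assume an odds ratio of 1.5 to 2.5 per SD, equal in both arms. For a logistic model with a standard normal covariate, R² = Var(E[Y|X]) / (p(1 − p)). The half-width is multiplied by √(1 − R²), and the equivalent number of extra women is 154 × R²/(1 − R²). Power is simulated for 30% against 15% failure with 77 per arm (1,500 trials per setting), chi-square against the adjusted Wald test.

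| OR per SD | R² at 30% failure | Extra women | Half-width (points) | Power, unadjusted to adjusted |
|---|---|---|---|---|
| 1.5 | 0.033 | 5.3 | 14.2 | 63% to 63% |
| 2.0 | 0.087 | 14.7 | 13.8 | 62% to 64% |
| 2.5 | 0.137 | 24.4 | 13.5 | 60% to 65% |

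A repeat with 4,000 trials per setting gave gains of 0.8, 2.3 and 4.5 points. Across all runs of this scenario the gain was about 0 to 6 points, and the simulated standard error of the standardised risk difference fell by 1-6%. For 30% against 50% failure, power went from 71.4% to 73.6% at OR 1.5 and from 73.8% to 77.1% at OR 2.0, with no change at OR 1.3.

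**If PVR predicts failure in the traditional arm only.** With 30% against 15% failure, adjusted minus unadjusted power was −1.0, −0.3 and +1.0 points for OR 1.5, 2.0 and 2.5. Further runs gave roughly nil to 2 points.

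**If PVR is not prognostic.** The loss is about 1 power point or less.

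**Scale of the result.** In these simulations, adding PVR raised the standard error of the log odds ratio by 2%, 5% and 9%. A conditional odds ratio does not gain a narrower interval from adjustment. The interval narrows for the standardised risk difference.

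**The case against.** The strongest reply is that this is a preference about a supporting model. The plan already schedules an adjusted regression for each of the three aims, and its open list does not exclude PVR. The outcomes are secondary. The assumed odds ratio carries the whole calculation. The link to baseline emptying is also doubtful in the FAST arm: under section 11 a woman with a VAS of 50 or more passes with no PVR measured, and one with a lower score still passes if her PVR is below 500. The power scenario of 30% against 15% is illustrative, since the plan expects about 30% failure in both arms. All of this stands, and it limits the size of the point.

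What it does not answer is that the lead test for aim 2a ignores the strata, and that an open list is not prespecification.

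A reader might infer three stronger things that the documents do not support:

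- **That every woman has a recorded preoperative PVR.** The value is chart data, with no required baseline measurement and no statement of completeness. Dropping women without it could cost more precision than adjustment gains.
- **That the plan has no adjusted analysis of these aims.** It has one, ranked as secondary.
- **That a known amount of precision is being lost.** Without a prognostic strength in the documents, the gain could be negligible.

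**Conclusion.** The point holds as a modest improvement to aim 2a, not as an error that threatens the trial. PVR is listed for collection and named in no model; the lead test for aim 2a is unadjusted and ignores site and surgery type; the adjusted model is secondary with an open list. The expected gain is about 0 to 6 power points and a 1-6% smaller standard error for the risk difference. This assumes an odds ratio of 1.5 to 2.5 per SD that is equal in both arms, and that the listed PVR is preoperative and largely available. The gain is close to nil if PVR predicts failure only in the traditional arm. For aims 2b and 2c events may be too few for an adjusted model to lead. The primary non-inferiority conclusion does not depend on any of this.

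**What to change.** In section 12:

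1. Make the lead analysis for aim 2a a logistic model with voiding group, site, surgery type, age and continuous preoperative PVR. Report a standardised risk difference with a 95% confidence interval, and state how its variance is obtained. Keep the chi-square or Fisher's exact test as a sensitivity analysis.
2. State a simple rule for missing PVR, for example single imputation from baseline data plus a missing-value indicator, so that no randomised evaluable woman is dropped.
3. For aims 2b and 2c, keep the unadjusted test as lead and name PVR in the supporting logistic model. Replace the open covariate list with a fixed one.
4. In section 11, say that the PVR in the chart-data list is the preoperative value.

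The cost is a few sentences and some programming for the standardisation and imputation. No women, visits or procedures are added. The statistical price is about 1 power point or less if PVR proves not to be prognostic, plus the handling of missing chart values.
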